There are two overall aims of this investigation. The first aim is to identify whether Exparel has an impact on postoperative pain and function following open treatment of hip fractures. The hypothesis is that injecting Exparel into the hip capsule and surrounding tissues will decrease narcotic use, and in turn decrease the risk of associated side effects including medically induced delirium, constipation, and decreased alertness. The second aim of the study is focused on examining whether increased pain control leads to better postoperative outcomes? When pain is better controlled via non-narcotic measures, overall patient comfort will improve while sparing cognitive function, decreasing time to ambulation, and accelerating progress with physical therapy. Quicker recovery times will then produce shorter hospital stays, which would yield better overall patient satisfaction and overall improved outcomes. Patients with intracapsular hip fractures will undergo hip hemiarthroplasty using a bipolar prosthesis placed via a posterior approach. Primary outcome measures include postoperative visual analogue scale (VAS from 0-10) pain scores at 12, 24, 36, 48 hours after surgery, time to ambulation with physical therapy, need for postoperative total morphine equivalent, and delirium scale measurements. Secondary outcomes measures will compare length of stay, discharge disposition (home or skilled nursing facility), 30-day readmission rates, and adverse events leading to ICU care or reoperation. All patients in both groups will have access to breakthrough pain medication which will either be Percocet for moderate to severe pain (pain scale of 4-10, acetaminophen or Toradol for mild to moderate pain (pain scale of 2-4).

Study Procedures

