There will be a total of 50 patients enrolled in this randomized blinded prospective two arm study. The participants will be randomized into either the control or the EXPAREL treatment group, with 25 patients in each cohort with the use of the randomization program available at randomizer.org. The injection of Exparel or a placebo will not change the surgical procedure being performed, the implants used, operative time, or rehab protocols and therefore do not alter the standard of care by participating in this study. The research design was formulated by the Orthopaedic Trauma Association in a recently-suspended call for research proposals; for the purposes of this study we will be performing a modified version of their requested protocol (please refer to the attached PDF).

Study Population

Inclusion criteria:

The inclusion criteria include men and women sixty-five years of age and older with isolated intracapsular hip fractures undergoing hemi arthroplasty through a posterior approach with the ability to consent to the study.

Exclusion criteria

Patients will be excluded if they have an extracapsular hip fracture, suffer from any form of cognitive compromise that leaves them unable to consent, or if they are treated with any surgical modality other than hip hemiarthroplasty.

Study Drugs or Devices:

The only drug that will be used in this Exparel. Exparel is FDA approved for local infiltration in to wound for postoperative pain relief. No IND number will be required.

Study Instruments (e.g., Questionnaires, Interview Outlines, Focus Group Guides

Does the delivery of Exparel into hip capsule during hemiarthroplasty will affect the following primary outcome measures?

1. Decreased pain on a postoperative visual analogue scale (VAS) pain scores at 12, 24, 36, 48 hours after surgery
2. There will be a decreased time to ambulation with physical therapy
3. There will be a decreased need for postoperative total morphine equivalent

Does the delivery of Exparel into hip capsule during hemiarthroplasty affect any of the following secondary outcome measures:

1. Decrease. Delirium scale measurements.
2. Decreased length of stay

We will also look record:

1. Discharge disposition (home or skilled nursing facility)

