The following primary outcomes will be recorded for each patient post-op day 1: -Delirium Scale (CAM)- Total morphine equiv. post-surgery (Oral Percocet will be converted into morphine equivalents and pain score will be recorded at the time of administrating narcotics.

VAS pain scores combined with and 11 point numerical rating scale (NRS) for subjective pain at 4, 8, 12, 24, and 48, hours after surgery.

Time to ambulate with physical therapy.

The following secondary outcomes will also be recorded for each patient from post-op day until discharge/readmission:

- Length of stay
- discharge disposition (home vs. skilled nursing vs. inpatient rehab)

The orthopaedic surgery team routinely grades pain postoperatively and uses a standardized pain scale to address patient's pain. The pain scales and primary outcomes will be recorded by the blinded orthopaedic research resident who does not participate in surgical procedures or have clinical responsibilities, but is familiar with and has previously utilized all of these systems.

[name], anesthesiologist at Maimonides Medical center, performed a similar study at our center using Exparel vs. a saline control injected into the posterior knee capsule in patients undergoing total knee arthroplasty. Therefore, collaboration with the Anesthesia Department, which has already completed a similar study, allows us to adopt their methodology for this study. Both the patient and the researcher following the patient postoperatively will be blinded. While the treating surgeon will be able to notice the difference between the placebo and Exparel, the outcomes outlined above will be recorded by the blinded Orthopaedic Research Resident who has no clinical responsibilities during his/her year of research and does not participate in operative procedures.

Study Protocol

Subjects will be divided into two groups, A and B. Group A (saline control) will receive 20 ml of saline mixed with 40cc 0.25% bupivacaine while group B (study) will receive 20 cc of Exparel mixed 40cc 0.25% bupivacaine. Multimodal analgesia will be used to supplement pain control. Each patient will receive 1g Tylenol (not to exceed 4g in 24 hours). All subjects will have access to rescue analgesics. Oxycodone 5mg q4 PRN for moderate pain (4-<7, and Morphine 2mg q4 PRN for severe breakthrough pain (Pain score of 7 or greater).

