The technique was modified from the protocol of [name]: Once implants are in place and confirmed to be appropriately placed by full arc range of motion, wound will be copiously irrigated, and final hemostasis is obtained. The control group involved injection of 40 cc of 0.25% bupivacaine HCl (Marcaine) with 20 cc of normal saline injected in a systematic fashion with self-retaining retractors exposing the surgical field. Multiple 20cc syringes with 22 gauge spinal needles are used. Starting medially and posteriorly, the capsule is injected circumferentially in 10-12 locations with 2-3cc in each location, watching for the capsule to swell slightly. The posterior capsule is injected around the neck of the implant. Care is taken to ensure that the needle only penetrates the capsule 1-2 cm to prevent sciatic nerve or femoral nerve injury. Any remaining solution is then used to inject the abductors, and tensor fascia lata. If any is remaining, the subcutaneous layer is injected. Post operative notes and charting will state "patient is a study patient and either Exparel or saline was administered" to preserve blinding.

After 25 patients are enrolled, the study will be paused and an update provided to the IRB.

Statistical Analysis

Descriptive summary statistics (means, standard deviations, ranges, etc.) for each of the endpoints will be produced for all subjects. The dose of all opioids administered will be converted into morphine equivalents for analysis. Since this is a two-sided analysis with continuous variables, the T-test will be performed on pain scores and morphine equivalents comparing Exparel to saline where an α of 0.05% will be considered significant. The duration of post analgesia observed with EXPAREL will be compared with saline controls receiving. Additionally, the incidence of postsurgical AEs will be summarized for all subjects.

Power analysis

We performed 2 power analysis.

Presuming that pain scores are normally distributed, and equal standard deviations, 1:1 ratio of people in each group, alpha=.05, Power=.80 the sample size per group will vary by the projected mean difference between groups and the standard deviation. The table below give you a few different calculations for a simple T-Test difference between two independent groups.

Keep in mind that these estimates are only for a simple t-test. As you look to do multivariate analyses you will need much more to allow for additional analyses and incomplete or problem data.

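### Pre-fracture opioid use is neither an exclusion nor a recorded item, so the unadjusted comparison of total morphine equivalents loses precision and a chance imbalance cannot be checked

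*Combined protocol and SAP*

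**What the plan says.** Inclusion criteria (Study Population) cover consenting patients aged 65 or over whose isolated intracapsular fracture is treated by hemiarthroplasty from a posterior approach. Exclusion criteria name three things. Two are in this part of the sentence: "Patients will be excluded if they have an extracapsular hip fracture, suffer from any form of cognitive compromise that leaves them unable to consent". The third is treatment by another kind of operation. Neither list mentions opioid use.

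Opioid consumption is a primary outcome in three places. Description of Outcome Measures includes "need for postoperative total morphine equivalent, and delirium scale measurements" among the primary measures. Study Instruments lists "There will be a decreased need for postoperative total morphine equivalent" as the third primary outcome, and its list of items to record has "Total morphine equiv. post-surgery (Oral Percocet will be converted into morphine equivalents and pain score will be recorded at the time of administrating narcotics". That item covers the period after surgery only. No baseline medication or opioid history is listed anywhere.

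Statistical Analysis states that "The dose of all opioids administered will be converted into morphine equivalents for analysis" and that "the T-test will be performed on pain scores and morphine equivalents comparing Exparel to saline". It names no covariate. Study Procedures assigns 25 patients to each arm through an online randomisation program and mentions no stratification.

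**The concern.** The protocol's hypothesis is that the injection reduces narcotic use. An opioid taken for long-standing pain is not a response to the operation or to the injection. If it is given during the admission, a total of all opioids administered includes it. A few such patients could sit well above the rest, widen the spread of a primary outcome, and fall unevenly between two arms of 25. If prior use is never recorded, the trial data cannot show whether this happened, and neither adjustment nor a sensitivity analysis is possible.

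**Working it through.** **The plan's own figures.** Power analysis gives power of .99 for a difference of 2, SD 1.5 and 25 per arm. The standardised effect is 2/1.5 = 1.33, and the two-sided t-test at 0.05 has power 0.996, so the figure reproduces. The second statement (difference 3, SD 2.2) has 3/2.2 = 1.36 and power 0.997. The effect size printed there as a minimum, 0.90, gives 0.877. All of these concern pain scores. The plan has no power figure for morphine equivalents.

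**Assumptions, none of them in the documents.**
- A proportion p of patients are prior users: 5%, 10% or 20%.
- Users' totals lie k SD above the rest, in units of the non-users' SD: k = 1 to 4. The excess is unaffected by the injection.
- The treatment effect is 0.90 SD or 1.36 SD, both borrowed from the pain-score statement.
- Alpha is 0.05 two-sided, as in Power analysis. Statistical Analysis prints 0.05%, which is a separate matter.

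**Loss of precision.** The outcome SD is multiplied by √(1 + p(1−p)k²). For p = 0.10, k = 2 this is √(1 + 0.09 × 4) = 1.17. For p = 0.20, k = 4 it is √(1 + 0.16 × 16) = 1.89. Dividing the effect by this factor approximates the power; simulation with 25 per arm agrees within about one percentage point. For an effect of 0.90 SD (88% with no users), unadjusted:

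| Users | k = 1 | k = 2 | k = 3 | k = 4 |
|---|---|---|---|---|
| 5% | 86% | 81% | 74% | 66% |
| 10% | 85% | 76% | 64% | 52% |
| 20% | 82% | 68% | 51% | 38% |

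With an effect of 1.36 SD the same grid runs from over 99% down to about 70%.

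**With a yes/no prior-use covariate, effect 0.90 SD.** If every user has the same excess, power is about 87% in every cell. If the excess varies between users (lognormal, CV 0.5), adjusted power over k = 1 to 4 is 83–87% at 5% users, 77–86% at 10% and 67–86% at 20%. In the worst of these cells (20%, k = 4) the unadjusted test has 34%, so adjustment recovers (67 − 34)/(88 − 34) = 61% of the loss. With CV 1 that cell has 32% unadjusted and 49% adjusted, so (49 − 32)/(88 − 32) = 30% is recovered.

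**Chance imbalance.** With the number of users in each arm binomial (25, p):

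| Users | Arms differ by 2 or more | By 3 or more |
|---|---|---|
| 5% | 31% | 10% |
| 10% | 47% | 23% |
| 20% | 59% | 37% |

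An imbalance of m users shifts the arm difference by mk/25. For m = 2, k = 2 this is 0.16 SD; for m = 3, k = 4 it is 0.48 SD. The standard error with no users is √(2/25) = 0.28 SD, and the difference needed for significance is 2.01 × 0.28 = 0.57 SD.

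**Type I error.** With no treatment effect, p from 0 to 20% and k from 2 to 4, the unadjusted t-test rejects in 4.5–5.2% of simulated trials.

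**The case against.** The strongest reply is that randomisation already deals with this. For validity it does: prior users are balanced in expectation, and the type I error is intact. A reader might infer that an imbalance of two or three users is enough to manufacture a positive result. The figures do not support that in general. With the split held at 0 v 2, 1 v 3, 1 v 4 or 2 v 5 users, the false-positive rate is 4–8%; only 0 v 3 raises it to 10–16%. Those splits are already averaged into the overall 5%. What randomisation does not do is restore precision, or make an imbalance visible when the variable is missing.

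The second reply is that the size is assumed. That stands. Prevalence and excess are not in the documents, and 0.90 is a minimum stated for a pain score. At an excess of 1 SD the loss is at most about six points (88% to 82%).

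Third, the plan does not say that home opioids continue in hospital. The analgesics it names are the study regimen and rescue drugs. Including home doses is an inference from the wording that all administered opioids are converted. Nor does the plan say that allocation is simple randomisation; it only mentions no stratification.

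Fourth, broad eligibility is a legitimate choice, and the PDF that Study Procedures calls attached is not available here. It could hold more criteria, but the protocol describes its design as a modification and states its own criteria. Power analysis also warns that multivariate analyses need more patients; one covariate costs one degree of freedom.

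**Conclusion.** The point holds as one of precision and baseline recording. Regular opioid users are eligible, their prior use is not a listed item, and a primary outcome that counts all opioids is tested without adjustment in 25 per arm. It does not show bias or an inflated false-positive rate, and it does not make the comparison invalid.

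The loss could be negligible or serious: about 86% down to 38% power against 88% without users if the effect is 0.90 SD, and over 99% down to about 70% if it is 1.36 SD. The low ends need 20% users at 4 SD above the rest and should not be read as expected values. A reader might also infer that a yes/no covariate restores full power whatever the doses. That is true only if all users have the same excess; with variable excess the recovery is partial. This is a cheap improvement, not a fault that undermines the trial.

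**What to change.** 1. Add to the items recorded at enrolment, taken from the admission medication list: regular opioid use before the fracture (yes/no) and the daily dose in morphine equivalents.
2. In Statistical Analysis, replace the unadjusted t-test for morphine equivalents with a linear model containing treatment and prior opioid use. Name one form of the covariate before outcome data are seen: yes/no, or the baseline daily dose with zero for non-users. The dose form is the natural choice if doses are expected to differ widely.
3. Tabulate prior use by arm with the other baseline data.

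The cost is one entry on the case-report form and one degree of freedom. It needs no extra patients or visits and no change to eligibility or treatment.

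### Time to ambulation is a primary outcome with no between-arm test, an ambiguous observation window and no rule for patients who have not walked

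*Combined protocol and SAP*

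**What the plan says.** Time to ambulation with physical therapy is called primary in three places: in Description of Outcome Measures, in the numbered primary list under Study Instruments ("There will be a decreased time to ambulation with physical therapy"), and in the list of outcomes to be recorded that follows in the same section ("Time to ambulate with physical therapy").

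That last list opens with "The following primary outcomes will be recorded for each patient post-op day 1". Ambulation appears below this line, but so do pain scores "for subjective pain at 4, 8, 12, 24, and 48, hours after surgery". The next block has an open-ended window: "The following secondary outcomes will also be recorded for each patient from post-op day until discharge/readmission".

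Statistical Analysis promises "Descriptive summary statistics (means, standard deviations, ranges, etc.) for each of the endpoints will be produced for all subjects". For comparison between arms it says that "the T-test will be performed on pain scores and morphine equivalents". No section states when the ambulation clock starts, what counts as ambulation, when observation ends, what to do with a patient who has not walked by then, or which test applies.

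**The concern.** There are two gaps. First, followed as written, the plan has no between-arm comparison for one of its primary outcomes, although the second aim of the study rests on better pain control leading to earlier walking.

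Second, a mean is a poor summary for a time that some patients may never reach under observation. The trial enrols hip-fracture patients aged 65 or older and lists skilled nursing and inpatient rehabilitation among the discharge destinations, so some may be unable to walk with therapy before observation ends. They have no value to average. If only observed times are used, exclusion depends on the outcome itself and falls more heavily on the slower arm. The subsets compared are then no longer the randomised groups, and a true benefit is understated. If the method is chosen after the data are seen, the choice can also follow the result.

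**Working it through.** **The plan's own figures.** None concerns ambulation. The stated power of .99 in Power analysis is for pain scores (25 per arm, difference 2, SD 1.5, alpha 0.05). It reproduces: 0.997 by the normal approximation and 0.996 by the exact t calculation. It says nothing about time to walking.

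**Assumed inputs.** Median time to ambulation 24 h with Exparel and 36 h with control; two shapes, exponential and Weibull with shape 2; cut-offs of 24, 48 and 120 h. All are illustrative, because the documents give no ambulation times.

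**Formula.** With S(t) the proportion not yet walking at time t, the mean among those who have walked by c is

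E[T | T ≤ c] = (∫₀ᶜ S(t) dt − c·S(c)) / (1 − S(c)).

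For exponential times with median m this becomes m/ln 2 − c·S(c)/(1 − S(c)), where S(c) = 2^(−c/m).

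**Exponential, 48 h cut-off.**
- True means: 24/ln 2 = 34.6 h and 36/ln 2 = 51.9 h; difference 17.3 h.
- Not walking at 48 h: 2^(−48/24) = 0.250 (Exparel) and 2^(−48/36) = 0.397 (control).
- Walkers-only mean, Exparel: 34.62 − 48 × 0.250/0.750 = 18.62 h.
- Walkers-only mean, control: 51.94 − 48 × 0.397/0.603 = 20.35 h, carrying full precision.
- Difference 1.73 h, and 1.73/17.31 = 10% of the true difference.

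**Weibull shape 2, 48 h cut-off.** True means are 25.5 h and 38.3 h, a difference of 12.8 h. Not walking at 48 h: 6% and 29%. Walkers-only means are 23.5 h and 28.0 h, a difference of 4.5 h, or 35% of the true difference.

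**All three cut-offs, medians 24 h and 36 h.**

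| Cut-off | Exponential: walkers-only difference (share of 17.3 h) | Weibull: walkers-only difference (share of 12.8 h) |
|---|---|---|
| 24 h | 0.5 h (3%) | 0.6 h (5%) |
| 48 h | 1.7 h (10%) | 4.5 h (35%) |
| 120 h | 8.0 h (46%) | 12.7 h (almost 100%) |

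**Other assumed medians.** Adding 16 vs 24 h, 24 vs 48 h and 36 vs 48 h (Exparel vs control), the share kept is 1–16% at 24 h and 5–77% at 48 h. At 120 h it is 27–72% under exponential times and 92–100% under Weibull times.

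**Power.** Simulation with 25 per arm, 1,500 runs, medians 24 h and 36 h, two-sided 0.05. The log-rank test censors non-walkers at the cut-off.

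| Cut-off | Exponential: walkers-only t-test / log-rank | Weibull: walkers-only t-test / log-rank |
|---|---|---|
| 24 h | 0.05 / 0.17 | 0.06 / 0.41 |
| 48 h | 0.07 / 0.22 | 0.23 / 0.73 |
| 120 h | 0.17 / 0.29 | 0.77 / 0.80 |

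The log-rank test does better in every row. The gain is large when many patients are still not walking at the cut-off and small when nearly all have walked.

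**The case against.** The strongest reply is that the plan never commits itself to the harmful analysis. Three stronger readings are tempting, and the documents support none of them as fact.

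- **That recording stops on day 1.** The same heading stands above pain scores to 48 hours, so it cannot literally bound everything beneath it, and its scope may be a matter of layout. Elsewhere the outcome is stated without a day 1 limit. What stands is the ambiguity: the secondary outcomes have a window to discharge or readmission, and this primary outcome has no clear one.
- **That patients who have not walked are dropped.** No section says so; the summaries are promised for all subjects, and the open-ended list of statistics leaves room for medians or proportions. What stands is that a mean over all subjects cannot be computed without a censoring or imputation rule, and none is given.
- **That the difference between arms would largely vanish.** This needs an early cut-off, walkers-only means and many patients still not walking at that point. It also depends on the shape of the distribution: exponential times, with their long right tail, are an unfavourable case. With follow-up to about 120 h and Weibull times there is almost no loss.

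The proportion discharged without having walked is also unknown. None of this supplies the missing test, window or rule.

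**Conclusion.** The point holds in a conditional form. What the text establishes is that a primary outcome has no named between-arm comparison, an unclear observation window, and a summary that is undefined for patients who have not walked.

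The bias is conditional on averaging walkers only. In that case it runs toward no difference in every scenario examined. Its size cannot be fixed from the documents: under the assumed medians of 24 h and 36 h, about 10% to 35% of the true mean difference survives a 48 h cut-off, and about half to nearly all survives 120 h. It would be wrong to report that the protocol excludes slow patients or that a real effect would necessarily be lost. The change should be made because it is cheap and closes all three gaps on any reading of the heading.

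**What to change.** In the list of outcomes to be recorded under Study Instruments, take time to ambulation out of the post-op day 1 group. Define it as hours from end of surgery to first ambulation with physical therapy, say what counts as ambulation, and follow each patient to discharge.

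In Statistical Analysis, replace the mean for this outcome with a time-to-event comparison of all randomised patients: Kaplan-Meier medians and a two-sided log-rank test. Keep patients who die or are discharged before walking in the analysis as not having walked, censored at a common prespecified time, so that early discharge to a facility does not count in an arm's favour. State the significance level with the test, since this section prints "an α of 0.05% will be considered significant" while Power analysis uses .05.

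The cost is a few sentences of protocol text; the times should already be in the physical therapy notes. There are two downsides. A median and a log-rank result replace a mean difference; a restricted mean time would be a reasonable alternative if a difference in hours is wanted. The convention for patients discharged before walking treats unobserved time as time not walking; that is an assumption and should be stated as one. Both changes should be settled before any unblinded data are seen.

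### Pain is scored four or five times per patient but tested by a bare t-test with no stated unit of analysis; unadjusted testing at each time carries about a 13–21% chance of a false-positive pain result

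*Combined protocol and SAP*

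**What the plan says.** The Description of Outcome Measures section lists "visual analogue scale (VAS from 0-10) pain scores at 12, 24, 36, 48 hours after surgery" first among the primary outcomes, and the list of primary outcomes under Study Instruments gives the same four times. Later under Study Instruments, the outcomes to be recorded have pain at five times: 4, 8, 12, 24 and 48 h. The same list says, within the item on morphine equivalents, that a "pain score will be recorded at the time of administrating narcotics".

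The whole inferential plan for pain is one sentence in Statistical Analysis: "Since this is a two-sided analysis with continuous variables", "the T-test will be performed on pain scores and morphine equivalents comparing Exparel to saline", with an α "of 0.05% will be considered significant". It names no time point, per-patient summary, repeated-measures model, multiplicity rule or rule for missing scores. The Power analysis section works with one value per patient: "Presuming that pain scores are normally distributed, and equal standard deviations, 1:1 ratio of people in each group, alpha=.05, Power=.80". It warns that its estimates cover a simple t-test only.

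**The concern.** A two-sample t-test needs one independent value per patient. This trial collects several correlated ones, and the plan does not say how they become one. That leaves an analyst free to test each time, pool all scores or average them, after seeing the data, on the first-listed primary outcome of a 50-patient trial.

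The two literal readings both have a cost. Testing each time without adjustment gives four or five chances of a positive pain result, and each test discards what the same patient's other scores say. Pooling treats correlated scores as independent, so the standard error is too small. The point is how repeated scores enter the test, not which outcome should be primary.

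**Working it through.** **Inputs from the documents.** 25 per arm ("with 25 patients in each cohort", Study Procedures); two-sided test; alpha .05 (Power analysis); m = 4 or 5 scheduled scores; planning cases of 1.5 points with SD 2, 2 points with SD 1.5, and 3 points with SD 2.2 (Power analysis).

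**Assumed.** Within-patient correlation ρ of 0.3 to 0.7, equal between any two times. The documents give no value.

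**1. The plan's own figures.** A two-sided t-test at 0.05 with 80% power needs 16.7, 8.1, 63.8 and 28.9 per group for the four table rows; the plan states 17, 8, 65 and 29. Power at 25 per group is 0.996 for 2 points/SD 1.5 (stated .99) and 0.997 for 3 points/SD 2.2 (stated above 90%). At the literal 0.05% these would be 0.825 and 0.850. The stated power therefore rests on .05, which is used below. (The effect size of .90 printed beside the last case is not 3/2.2 = 1.36; at .90 power would be 0.877.)

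**2. Test at each time, no true effect.** Each test holds 5%. If times were independent, the chance of at least one false positive would be 1 − 0.95⁴ = 18.5% or 1 − 0.95⁵ = 22.6%. Correlation lowers it. Simulation (10,000 trials per cell, 25 per arm):

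| Times | ρ = 0.3 | ρ = 0.5 | ρ = 0.7 |
|---|---|---|---|
| 4 | 17.6% | 16.2% | 12.5% |
| 5 | 20.8% | 18.6% | 15.2% |

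**3. All scores pooled, no true effect.** The variance is understated by the factor D = 1 + (m − 1)ρ, so the false-positive rate is 2[1 − Φ(1.96/√D)]. For m = 4 and ρ = 0.5, D = 2.5, 1.96/1.581 = 1.240, and the rate is 21.5%.

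| Scores | ρ = 0.3 | ρ = 0.5 | ρ = 0.7 |
|---|---|---|---|
| 4 | 15.5% | 21.5% | 26.6% |
| 5 | 18.6% | 25.8% | 31.5% |

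Simulation agrees (15.9–26.4% and 18.2–31.6%). At the literal alpha of 0.05%, pooling gives 1.2–7.4%, and per-time testing at most 5 × 0.05% = 0.25%.

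**4. One mean per patient.** The simulated false-positive rate of a t-test on per-patient means was 4.4–5.4%, that is, nominal. Any weights fixed in advance also give one independent value per patient. Trapezoidal time weights are 6, 12, 12, 6 over 36 for the four-time schedule (Σw² = 0.278) and 2, 4, 8, 18, 12 over 44 for the five-time schedule (Σw² = 0.285). Relative to a single score, the variance of the mean is ρ + (1 − ρ)Σw²:

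- ρ = 0.5: 0.639 or 0.643. SD = 2 × √0.64 = 1.60.
- ρ = 0.7: 0.783 or 0.786. SD = 2 × √0.784 = 1.77.

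For 1.5 points at every time, the standardised difference rises from 1.5/2 = 0.75 to 0.94 or 0.85. Power at 25 per arm rises from 74% to about 90% or 83%.

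**5. Effect not constant over time.** The mean beats a single-time test only if the average effect exceeds √0.64 = 0.80 (ρ = 0.5) or √0.784 = 0.89 (ρ = 0.7) of the effect at that time. Suppose 1.5 points appears only from 24 h.

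- Five-time schedule: the late weights are (18 + 12)/44 = 0.682, so the mean difference is 1.02. Standardised, this is 1.02/1.60 = 0.64 or 1.02/1.77 = 0.58. Power is about 60% or 52%, against 74% at one late time.
- Four-time schedule: the late weights are 30/36 = 0.833, so the difference is 1.25. Power is about 77% or 69%.

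**The case against.** **Pooling is not the stated plan.** A reader might infer that the trial will pool scores and so run a false-positive rate of 20–30%. The documents do not support that. The outcome is defined at named times ("pain scores at 12, 24, 36, 48 hours after surgery"), and power is computed with patients as units. Pooling remains possible only because the analysis sentence does not exclude it, and its rate depends on an assumed correlation. This objection stands, which is why the per-time reading comes first.

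**Dose-time scores.** A reader might also infer that scores taken at opioid doses enter the pain test and over-weight patients in most pain. They are mentioned inside the morphine-equivalent item, apart from the scheduled pain scores, and nothing puts them in the test. No figure above includes them. They matter only as something to exclude explicitly.

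**Power is adequate for the differences the plan expects.** This is correct: above 99% for 3 points/SD 2.2 and for 2 points/SD 1.5, even at one time. The gain from averaging is material only for smaller differences, such as the plan's own 1.5 points with SD 2, for which it asks 29 per group and has 25.

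**Averaging is not free.** This also stands. The mean estimates a different quantity, average pain over follow-up. The rationale describes extended drug release, and the Study Protocol section puts bupivacaine in both injections (Research Design and Methods describes the control differently; those passages must be reconciled). A later-emerging difference is therefore plausible, and step 5 shows that power can then fall.

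**Other methods would do.** A mixed model for repeated measures with one prespecified contrast would also make the patient the unit. The mean is suggested because it keeps the planned t-test.

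**Conclusion.** The gap is real: several scheduled scores per patient, one t-test, and no rule connecting them. On the likelier per-time reading, the chance of at least one false-positive pain result is about 13–21% if any significant time may be claimed. If scores were pooled, the rate would be about 16–32%. Both ranges rest on an assumed correlation of 0.3–0.7 and on alpha 0.05; at the 0.05% printed in the analysis section they would be far smaller, so the alpha conflict has to be settled first.

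The documents do not support saying that the trial is underpowered for the differences it expects, or that averaging always gains power. The case for one value per patient is mainly that it fixes the analysis in advance and holds the error rate. Better precision is a second benefit when the effect is broadly similar over time. The change should be made, and it does not call the design into question.

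**What to change.** 1. Reconcile the two pain schedules and the two alphas (0.05% in Statistical Analysis, .05 in Power analysis). The mean cannot be defined until there is one schedule.
2. In Statistical Analysis, state that the patient is the unit of analysis, and that pain is analysed as each patient's time-weighted mean of the scheduled scores, one value per patient, by the planned two-sided two-sample t-test.
3. State before unblinding how missing scores enter the mean, including how many scheduled scores a patient must have.
4. State that scores taken at narcotic dosing are not part of this mean, because their number and timing depend on pain and opioid use.
5. Show each scheduled time by arm with the difference and its confidence interval, as description only.

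The cost is wording: no extra patients, visits or data. The price is dilution of an effect limited to some times, down to about 52–60% power in the late-only example above against 74% at a single late time. The by-time display keeps such a pattern visible but does not test it. If the investigators expect a late effect, they should choose the averaging window with that in mind before any unblinded data are seen.
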